### **Proportion of subjects with SwCl <30 mmol/L through Week 24 (pooled with data from Study 102):**

The estimand and analysis will be similar to that for the pooled analysis of proportion of subjects with SwCl <60 mmol/L through Week 24.

#### **8.3.2.3 Multiplicity Adjustment**

A hierarchical testing procedure will be used to control the overall type I error at an alpha of 0.05. The key secondary endpoints will be formally tested at an alpha level of 0.05 only if the primary analysis of absolute change from baseline in ppFEV1 through Week 24 is statistically significant, i.e., if the null hypothesis of inferiority has been rejected. For a test at any step to be considered statistically significant within the testing hierarchy, it must be statistically significant, and all previous tests (if any) within the hierarchy must be statistically significant at the 0.05 level (one-sided 0.025 level for the primary endpoint). The testing order of the key secondary endpoints is as follows:

- Absolute change from baseline in SwCl through Week 24
- Proportion of subjects with SwCl <60 mmol/L through Week 24 (pooled with data from Study 102)
- Proportion of subjects with SwCl <30 mmol/L through Week 24 (pooled with data from Study 102)

#### **8.3.3 Analysis of Other Secondary Variables**

##### **8.3.3.1 Definition of Variables**

**Pulmonary exacerbation (PEX):** A PEX is defined as a new or change in antibiotic therapy (IV, inhaled, or oral) for any 4 or more of the following signs/symptoms:

- Change in sputum
- New or increased hemoptysis
- Increased cough
- Increased dyspnea
- Malaise, fatigue, or lethargy
- Temperature above 38°C (equivalent to approximately 100.4°F)
- Anorexia or weight loss
- Sinus pain or tenderness

- Change in sinus discharge
- Change in physical examination (PE) of the chest
- Decrease in pulmonary function by 10%
- Radiographic changes indicative of pulmonary infection

The number of PEx through Week 52 is defined as the total number of PEx during the PEx analysis period (defined in 8.1).

**Cystic Fibrosis Questionnaire – Revised (CFQ-R)**: The CFQ-R is a validated CF-specific instrument that measures quality-of-life domains. This study utilizes three different versions of CFQ-R:

- CFQ-R for Children Ages 12 and 13 (subjects 13 years and younger on the date of informed consent)
- CFQ-R for Adolescents and Adults (subjects 14 years and older on the date of informed consent)
- CFQ-R for Parents/Caregivers (subjects 13 years and younger on the date of informed consent)

In all three versions, specific questions belonging to a domain are scored 1, 2, 3, or 4. The CFQ-R domain score, e.g., physical domain score or respiratory domain score, is defined as a scaled score as follows:

Scaled score for a domain =  $100 \times (\text{mean (scores of all questions in the domain)} - 1)/3$ , where the score from a negatively phrased question is first reversed, i.e., reversed score =  $5 - \text{actual score}$ , so that 1 always represents the worst condition and 4 the best condition. The (scaled) domain score ranges from 0 (worst condition) to 100 (best condition). The scaled score for a specific domain will not be calculated if more than half of the questions in the domain have missing scores.

The (scaled) domain score from the CFQ-R for Children Ages 12 and 13 and for Adolescents and Adults will be pooled for analysis purposes.

### **8.3.3.2 Analysis Method**

**Number of PEx through Week 52**: The number of PEx through Week 52 will be analyzed, and the estimated PEx rate (per year, with 48 weeks as 1 year) will be presented. The difference in PEx rate and the associated 95% CI will also be provided.

**Absolute change from baseline in CFQ-R Respiratory Domain (RD) score through Week 24**: The analysis of absolute change from baseline in CFQ-R RD score through Week 24 will be based on an MMRM similar to the primary analysis of the primary estimand (8.3.1.3), with absolute change from baseline in CFQ-R RD score at Week 8, Week 16, and Week 24 as the dependent variable. The estimated treatment difference through Week 24 (estimated by averaging Weeks 16 and 24) will be presented along with the 2-sided 95% CI. The estimated within group change from baseline and treatment difference at each post-baseline visit, obtained from the model, will be provided.

**Absolute change from baseline in ppFEV1 through Week 52:** Analysis of this endpoint will be based on an MMRM similar to the primary analysis of the primary estimand (8.3.1.3), with the addition of data from Week 36 and Week 52. The estimated change through Week 52 will be based on averaging estimates from Weeks 16, 24, 36 and 52. The post-baseline raw values and the absolute change from baseline at each post-baseline visit through Week 52 will be summarized descriptively (n, mean, SD, median, min, max).

**Absolute change from baseline in SwCl through Week 52:** Analysis of this endpoint will be based on an MMRM similar to that for absolute change from baseline in SwCl through Week 24 (8.3.2.2), with the addition of data from Week 36 and Week 52. The estimated change through Week 52 will be based on averaging estimates from Weeks 16, 24, 36 and 52. The post-baseline raw values and the absolute change from baseline at each post-baseline visit through Week 52 will be summarized descriptively (n, mean, SD, median, min, max).

**Proportion of subjects with SwCl <60 mmol/L through Week 24 (within-study):** Analysis of this endpoint will be based on a GEE model similar to that for the proportion of subjects with SwCl <60 through Week 24 using the PFAS (8.3.2.2), but instead will be based on the FAS.

**Proportion of subjects with SwCl <30 mmol/L through Week 24 (within-study):** Analysis of this endpoint will be based on a GEE model similar to that for the proportion of subjects with SwCl <30 through Week 24 using the PFAS (8.3.2.2), but instead will be based on the FAS.

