### 8.3.1.3 Primary Analysis

The primary null hypothesis to be tested is that the mean for the primary efficacy variable for VNZ/TEZ/D-IVA is inferior by >3 percentage points compared to ELX/TEZ/IVA. The primary analysis of the primary estimand will be performed using a mixed-effects model for repeated measures (MMRM) with change from baseline at Day 15, Week 4, Week 8, Week 16, and Week 24 as the dependent variable. The model will include fixed categorical effects for treatment, visit, age at screening (<18 versus ≥18 years of age), genotype group (F/F, F/G, F/RF, TCR/non-F), and treatment-by-visit interaction, with baseline ppFEV1 and baseline SwCl as continuous covariates. The model will be estimated using restricted maximum likelihood. Denominator degrees of freedom for the *F*-test for fixed effects will be estimated using the Kenward-Roger approximation. An unstructured covariance structure will be used to model the within-subject errors. If the model estimation does not converge, genotype group will be considered with two levels (F/F and non-F/F) or removed from the model, and if non-convergence persists, an alternative covariance structure like compound symmetry will be used. Conditional on the observed data and covariates, missing data will be assumed to be missing at random (MAR).

The primary result obtained from the model will be the estimated treatment difference through Week 24 (estimated by averaging Weeks 16 and 24). The adjusted mean with a 2-sided 95% CI and the 1-sided *P* value for non-inferiority will be provided. The primary null hypothesis will be rejected, and non-inferiority demonstrated, if the lower bound of the CI is ≥-3.0.

The primary null hypothesis of non-inferiority described above will be tested based on the FAS.

If non-inferiority for the primary endpoint is demonstrated, and if the lower bound of the same 95% CI is greater than 0, then superiority for the primary endpoint is also demonstrated, and the 2-sided *P* value for superiority will be presented.

The estimated within-group change from baseline and treatment difference at each post-baseline visit, obtained from the model, will be provided. The estimated within-group change and its standard error (SE) at each post-baseline visit will also be plotted by treatment group.

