### 8.3.4.2 Analysis Method

**Proportion of subjects with SwCl <60 mmol/L through Week 52 (within-study):** Analysis of this endpoint will be based on a GEE model similar to that for the proportion of subjects with SwCl <60 through Week 24 using the FAS (8.3.3.2), with the addition of data from Week 36 and Week 52.

**Proportion of subjects with SwCl <30 mmol/L through Week 52 (within-study):** Analysis of this endpoint will be based on a GEE model similar to that for the proportion of subjects with SwCl <30 through Week 24 using the FAS (8.3.3.2), with the addition of data from Week 36 and Week 52.

**Absolute change from baseline in BMI at Week 52:** Analysis of this variable will be based on an MMRM similar to the primary analysis of the primary estimand (8.3.1.3). Data obtained from Day 15, Week 4, Week 8, Week 16, Week 24, Week 36, and Week 52 will be included in the model. The estimated treatment difference at Week 52 will be presented along with the 2-sided 95% CI. The post-baseline raw values and the absolute change from baseline at each post-

baseline visit through Week 52 will be summarized descriptively (n, mean, SD, median, min, max), in addition.

**Absolute change from baseline in BMI z-score at Week 52 (for subjects  $\leq 20$  years of age at Baseline)**: Analysis of this variable will be based on an MMRM similar to the primary analysis of the primary estimand (8.3.1.3), excluding the term age at screening ( $<18$  versus  $\geq 18$  years of age), for subjects  $\leq 20$  years of age at Baseline. Data obtained from Day 15, Week 4, Week 8, Week 16, Week 24, Week 36, and Week 52 will be included in the model. In case of convergence issues, genotype group may be removed or may be considered with two levels F/F and non-F/F. The estimated treatment difference at Week 52 will be presented along with the 2-sided 95% CI. The post-baseline raw values and the absolute change from baseline at each post-baseline visit through Week 52 will be summarized descriptively (n, mean, SD, median, min, max), in addition.

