**Absolute change from baseline in weight at Week 52**: Analysis of this variable will be based on an MMRM similar to the primary analysis of the primary estimand (8.3.1.3). Data obtained from Day 15, Week 4, Week 8, Week 16, Week 24, Week 36, and Week 52 will be included in the model. The estimated treatment difference at Week 52 will be presented along with the 2-sided 95% CI. The post-baseline raw values and the absolute change from baseline at each post-baseline visit through Week 52 will be summarized descriptively (n, mean, SD, median, min, max), in addition.

**Absolute change from baseline in CFQ-R RD score through Week 52**: Analysis of this domain will be based on an MMRM similar to that for absolute change from baseline in CFQ-R RD score through Week 24 (8.3.3.2), with the addition of data from Week 52. The estimated change through Week 52 will be based on averaging estimates from Weeks 16, 24, and 52. The estimated treatment difference through Week 52 will be presented along with the 2-sided 95% CI. The post-baseline raw values and the absolute change from baseline at each post-baseline visit through Week 52 will be summarized descriptively (n, mean, SD, median, min, max), in addition.

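### The SAP does not say that the CFQ-R RD, BMI, BMI z-score and weight models adjust for their own baseline; read literally they do not, at some cost in precision, mainly for CFQ-R RD.

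*SAP*

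**What the plan says.** SAP 8.3.1.3 lists the terms of the primary MMRM: treatment, visit, age group, genotype group, "and treatment-by-visit interaction, with baseline ppFEV 1 and baseline SwCl as continuous covariates". No other continuous covariate appears.

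Four further outcomes take their model from that section by reference:

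- **CFQ-R RD through Week 24** (8.3.3.2) is analysed "based on an MMRM similar to the primary analysis of the primary estimand (8.3.1.3), with absolute change from baseline in CFQ-R RD score" as the outcome. Its visits are given; its covariates are not.
- **CFQ-R RD through Week 52** (8.3.4.2) inherits that model: "Analysis of this domain will be based on an MMRM similar to that for absolute change from baseline in CFQ-R RD score through Week 24".
- **BMI and weight** (8.3.4.2) have the same opening: "Analysis of this variable will be based on an MMRM similar to the primary analysis of the primary estimand (8.3.1.3). Data obtained from Day 15". Visits follow, but no covariates.
- **BMI z-score** (8.3.4.2) is "similar to the primary analysis of the primary estimand (8.3.1.3), excluding the term age at screening". Removing the age term is the one stated change to the covariates, apart from a fallback for the genotype term if the model does not converge.

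The protocol (12.3.3.2 for the other secondary variables, 12.3.3.4 for the other endpoints) leaves these analyses to the SAP. Neither document says whether baseline CFQ-R RD, BMI, BMI z-score or weight is added, substituted or left out.

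**The concern.** SAP 8.1 defines absolute change as the post-baseline value minus the baseline value. Such a change is usually negatively correlated with its own baseline, because extreme baselines regress toward the mean. For ppFEV1 and sweat chloride this is dealt with, since both baselines are already in the primary model. When that model is carried to another outcome, the two covariates come along but the outcome's own baseline does not.

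Two things follow if the model is fitted as written. The confidence interval is wider than it need be, and a chance difference between arms at baseline feeds into the estimated difference with the opposite sign. Stratification (SAP 6.3) covers age, ppFEV1, sweat chloride, prior modulator use and genotype, so it does not directly balance CFQ-R, BMI or weight.

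There is also a specification problem. Two programmers could fit different covariate sets and both claim to follow the SAP. CFQ-R RD through Week 24 is a named secondary endpoint, to be reported as a treatment difference with a 95% CI, so its model should be fixed before unblinding.

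**Working it through.** **The plan's own figures.** The SAP states no power or precision for these four outcomes. Its two power statements do reproduce. With 275 × 0.9 = 247.5, taken as 247 evaluable per arm, power is 98.6% for ppFEV1 (SD 8, margin 3, true difference 0, 1-sided 0.025). It is 97.8% for sweat chloride (SD 14, difference 5, 2-sided 0.05). Both agree with the stated figure of more than 95%, and neither bears on the outcomes at issue.

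**Inputs.** The 247 per arm follows from SAP 6.2. The documents do not give the correlation r between an outcome's baseline and its follow-up value, or the share R² of own-baseline variance that baseline ppFEV1 and sweat chloride explain. Both are assumed and shown over a range. Equal SD s at baseline and follow-up is also assumed, and follow-up is treated as a single value.

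**Step 1: no help from ppFEV1 and sweat chloride.**

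- Variance of the change score without own baseline: 2s²(1 − r)
- Residual variance with own baseline: s²(1 − r²)
- Variance ratio, without to with: 2/(1 + r). The SE ratio is its square root, and 247 divided by the variance ratio is the effective number per arm.

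| r | Variance ratio | SE wider by | 247 per arm act like |
|---|---|---|---|
| 0.5 | 1.333 | 15.5% | 185 |
| 0.6 | 1.250 | 11.8% | 198 |
| 0.7 | 1.176 | 8.5% | 210 |
| 0.9 | 1.053 | 2.6% | 235 |
| 0.95 | 1.026 | 1.3% | 241 |
| 0.98 | 1.010 | 0.5% | 245 |

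I take r of 0.5 to 0.7 as plausible for CFQ-R RD, and 0.9 or more for BMI, BMI z-score and weight. The BMI z-score model covers only subjects aged 20 or under, so its numbers are below 247 per arm. The percentage loss does not depend on the number of subjects.

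**Step 2: partial help from ppFEV1 and sweat chloride.** If they act only through the outcome's own baseline, the variance ratio becomes [(1 − r)²(1 − R²) + (1 − r²)]/(1 − r²). With R² = 0.10:

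- r = 0.5: (0.25 × 0.9 + 0.75)/0.75 = 1.300, SE wider by 14.0%
- r = 0.7: (0.09 × 0.9 + 0.51)/0.51 = 1.159, SE wider by 7.6%
- r = 0.95: variance ratio 1.023, SE wider by 1.1%

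**Step 3: chance imbalance.** Without own baseline, a baseline difference of d SDs moves the estimate by −(1 − r)d SDs. The SD of d is √(2/247) = 0.09, so an imbalance at 1.96 times that is 0.18 SD. It moves the estimate by about 0.09 SD at r = 0.5 and about 0.01 SD at r = 0.95, against the direction of the imbalance. As an illustration in CFQ-R points, an assumed 2-point imbalance at r = 0.6 moves the difference by (1 − 0.6) × 2 = 0.8 points.

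**Step 4: simulation check.** This used 4000 trials with 247 per arm, R² = 0.10 and a true difference of 0.

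| r | SE ratio, without to with | Correlation of estimate with imbalance, without | With |
|---|---|---|---|
| 0.5 | 1.137 | −0.46 | −0.01 |
| 0.7 | 1.074 | −0.35 | 0.01 |
| 0.95 | 1.012 | −0.16 | −0.01 |

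Both models averaged about 0, so neither is biased across randomizations. The SE ratios agree with Step 2.

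**The case against.** The strongest reply is that 'similar' is not 'the same', and that this SAP uses the word loosely. The pooled sweat chloride model in 8.3.2.2 has a genotype term that includes F/MF. The within-study version in 8.3.3.2 is described as similar, with only the analysis set changed. Study 103 has no F/MF group, so the genotype term must adapt without being told to. Own baseline could be taken as a further unstated adaptation.

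On the other side, the SAP does announce some changes: the age term is removed for BMI z-score and for the age subgroup in 8.3.1.5. A reader might infer that silence elsewhere means deliberate omission. The documents do not support that. Removing age from the z-score model has its own explanation, since the score is already adjusted for age and the population is restricted to age 20 or under. The same paragraph also repeats a genotype fallback that it would inherit anyway, so it is not a controlled list of departures. The text establishes that own baseline is unspecified, and absent if followed literally. It does not establish a decision to exclude it.

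Three more objections stand. Under randomization the change-score estimate is unbiased on average and its CI valid. The loss is small for three of the four outcomes. And all four lie outside the testing hierarchy (8.3.2.3), with confidence intervals but no P values planned. What remains is that nothing in the SAP directs the programmer to include the covariate, and including it is better under either reading.

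**Conclusion.** The point holds as a minor one. The own-baseline covariate is not specified for CFQ-R RD, BMI, BMI z-score or weight, and a literal fit omits it.

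For CFQ-R RD the standard error would then be about 8% to 15% wider at r of 0.7 to 0.5, or about 7.6% to 14% if ppFEV1 and sweat chloride explain 10% of baseline CFQ-R variance. For the other three it would be about 0.5% to 3% wider at r of 0.9 or more. These sizes rest on assumed correlations and on equal SDs at baseline and follow-up.

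A reader might infer that the CFQ-R result would be biased or its interval invalid, or that all four outcomes lose material precision. Neither follows. The dependence on chance imbalance is conditional on the imbalance observed and is part of the sampling variation that the interval already covers. The gain is material mainly for CFQ-R RD. No confirmatory test, power statement or sample size changes.

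**What to change.** In SAP 8.3.3.2 (CFQ-R RD through Week 24) and 8.3.4.2 (CFQ-R RD through Week 52, BMI, BMI z-score, weight), state that each MMRM includes the continuous baseline value of its own dependent variable as a covariate, in addition to baseline ppFEV1 and baseline sweat chloride.

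The cost is one sentence in each section, added before database lock and unblinding. There is no new data collection, and no subject is lost for want of that baseline, because the change score already requires it. One parameter is added to each model.

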## 8.3.4 Analysis of Other Endpoints

### 8.3.4.1 Definition of Variables

**Body Mass Index (BMI):** The BMI at each visit is calculated using the weight and height at each visit as follows:

$$\text{BMI} = \frac{\text{Weight (kg)}}{\text{Height}^2 \text{ (m}^2\text{)}}$$

**BMI z-score:** The BMI-for-age z-score, adjusted for age and sex, will be referred to as BMI z-score. The BMI z-score will be calculated using the Centers for Disease Control and Prevention (CDC) growth charts, with age (in months) used for the calculation defined in [Appendix](#) .

### 8.3.4.2 Analysis Method

**Proportion of subjects with SwCl <60 mmol/L through Week 52 (within-study):** Analysis of this endpoint will be based on a GEE model similar to that for the proportion of subjects with SwCl <60 through Week 24 using the FAS (8.3.3.2), with the addition of data from Week 36 and Week 52.

**Proportion of subjects with SwCl <30 mmol/L through Week 52 (within-study):** Analysis of this endpoint will be based on a GEE model similar to that for the proportion of subjects with SwCl <30 through Week 24 using the FAS (8.3.3.2), with the addition of data from Week 36 and Week 52.

**Absolute change from baseline in BMI at Week 52:** Analysis of this variable will be based on an MMRM similar to the primary analysis of the primary estimand (8.3.1.3). Data obtained from Day 15, Week 4, Week 8, Week 16, Week 24, Week 36, and Week 52 will be included in the model. The estimated treatment difference at Week 52 will be presented along with the 2-sided 95% CI. The post-baseline raw values and the absolute change from baseline at each post-

baseline visit through Week 52 will be summarized descriptively (n, mean, SD, median, min, max), in addition.

**Absolute change from baseline in BMI z-score at Week 52 (for subjects  $\leq 20$  years of age at Baseline)**: Analysis of this variable will be based on an MMRM similar to the primary analysis of the primary estimand (8.3.1.3), excluding the term age at screening ( $<18$  versus  $\geq 18$  years of age), for subjects  $\leq 20$  years of age at Baseline. Data obtained from Day 15, Week 4, Week 8, Week 16, Week 24, Week 36, and Week 52 will be included in the model. In case of convergence issues, genotype group may be removed or may be considered with two levels F/F and non-F/F. The estimated treatment difference at Week 52 will be presented along with the 2-sided 95% CI. The post-baseline raw values and the absolute change from baseline at each post-baseline visit through Week 52 will be summarized descriptively (n, mean, SD, median, min, max), in addition.

**Absolute change from baseline in weight at Week 52**: Analysis of this variable will be based on an MMRM similar to the primary analysis of the primary estimand (8.3.1.3). Data obtained from Day 15, Week 4, Week 8, Week 16, Week 24, Week 36, and Week 52 will be included in the model. The estimated treatment difference at Week 52 will be presented along with the 2-sided 95% CI. The post-baseline raw values and the absolute change from baseline at each post-baseline visit through Week 52 will be summarized descriptively (n, mean, SD, median, min, max), in addition.

**Absolute change from baseline in CFQ-R RD score through Week 52**: Analysis of this domain will be based on an MMRM similar to that for absolute change from baseline in CFQ-R RD score through Week 24 (8.3.3.2), with the addition of data from Week 52. The estimated change through Week 52 will be based on averaging estimates from Weeks 16, 24, and 52. The estimated treatment difference through Week 52 will be presented along with the 2-sided 95% CI. The post-baseline raw values and the absolute change from baseline at each post-baseline visit through Week 52 will be summarized descriptively (n, mean, SD, median, min, max), in addition.

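### The weight and BMI models give age one constant effect from Day 15 to Week 52, so the reported Week 52 confidence intervals are slightly wider than they need to be

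*SAP*

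**What the plan says.** The parent model in SAP 8.3.1.3 is specified as follows: "The model will include fixed categorical effects for treatment, visit, age at screening (<18 versus ≥18 years of age), genotype group" and so on, "and treatment-by-visit interaction, with baseline ppFEV 1 and baseline SwCl as continuous covariates". Treatment-by-visit is its only interaction. The covariance is unconstrained: "An unstructured covariance structure will be used to model the within-subject errors".

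SAP 8.3.4.2 carries this model to absolute change in weight and in BMI: "Analysis of this variable will be based on an MMRM similar to the primary analysis of the primary estimand (8.3.1.3"). It restates only the visits ("Data obtained from Day 15, Week 4, Week 8, Week 16, Week 24, Week 36, and Week 52 will be included in the model") and the contrast ("The estimated treatment difference at Week 52 will be presented along with the 2-sided 95% CI"). Neither paragraph changes the age term, so age has one coefficient for all seven visits.

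Three other facts matter. Protocol 8.1 admits subjects from age 12. SAP 6.3 stratifies randomisation by age under 18 versus 18 and over. SAP 5.4 lists weight and BMI at Week 52 as Other Endpoints, and SAP 8.3.2.3 leaves them out of the testing hierarchy.

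**The concern.** A constant age effect may suit ppFEV1. It does not suit body size followed for a year in a population that includes growing adolescents. Their extra gain over adults is near zero at Day 15 and largest at Week 52. If growth is linear and the extra gain is 4 kg at Week 52, it is 4 × 2/52 = 0.15 kg at Week 2 and 4 × 24/52 = 1.85 kg at Week 24. No single coefficient fits all of these.

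In a generalised least squares fit, the common coefficient is a weighted compromise across visits. If the variance of change grows with time, the early, precise visits dominate and the coefficient is small. Most of the Week 52 age difference then enters the Week 52 error variance, and from there the standard error of the one contrast reported. The 95% CI is the only inferential output planned for these endpoints, so its width is what is at stake.

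**Working it through.** **Inputs from the documents.** 275 per arm and 10% drop-out (SAP 6.2.1); seven visits, a main-effect age term and an unstructured covariance (SAP 8.3.1.3 and 8.3.4.2). The plan states no power, SD or precision for weight or BMI, so there is no figure of its own to reproduce here. As a check on the common inputs, 247 per arm (275 × 0.9), margin 3, SD 8 and 1-sided 0.025 give 98.6% power for ppFEV1, in line with the stated figure of more than 95%.

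**Assumed inputs.** p = share under 18; g = mean extra 52-week change in adolescents; s = within-age-group SD of change at Week 52.

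**Formula.** If the fitted common age coefficient is b, the Week 52 error variance rises from s² to about s² + p(1−p)(g−b)². The ratio of standard errors is

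√(1 + p(1−p)(g−b)²/s²),

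with a ceiling at b = 0 of √(1 + p(1−p)g²/s²).

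**Mid-range case: p = 15%, g = 4 kg, s = 4 kg.** I simulated 80 trials of 496 subjects (248 per arm), balanced on age, with complete data and random-walk weight change. Each was fitted with unstructured covariance, with and without age-by-visit.

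- The common age coefficient was 0.48 kg, against a true Week 52 difference of 4 kg.
- Week 52 error variance was 17.53 as planned and 15.93 with the interaction. The between-age-group variance is 0.15 × 0.85 × 4² = 2.04, so (17.53 − 15.93)/2.04 ≈ 0.79 of it stayed in the error term.
- SE as planned: √(2 × 17.53/248) = 0.376 kg. With the interaction: √(2 × 15.93/248) = 0.358 kg. The ratio is 1.049.
- The CI half-width is 1.96 × 0.376 = 0.74 kg against 1.96 × 0.358 = 0.70 kg.

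**Which standard error is right.** With the same age split in both arms, the age effect cancels from the treatment difference. Its sampling SD is √(2 × 4²/248) = 0.359 kg, which matches the interaction model and not the planned one. The spread of the estimates across the 80 trials was 0.403 kg under both models. That shows the two estimators coincide. With a standard error of about 0.403/√158 = 0.03, it cannot by itself separate 0.358 from 0.376.

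**Sensitivity to the covariance, same p, g and s.** Random subject slopes: 5.1% wider, coefficient 0.32 kg. Growth varying among adolescents with SD 2 kg: 4.8%. Equal variance at all visits: coefficient 1.6 kg, 37% of the variance left in the error term, and 2.4% wider.

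**Range for weight.**

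| p | g (kg) | s (kg) | Ceiling | Simulated ratio |
|---|---|---|---|---|
| 10% | 2 | 5 | 1.007 | 1.006 to 1.008 |
| 15% | 3 | 4 | 1.035 | about 1.03 |
| 20% | 4 | 4 | 1.077 | about 1.07 |
| 25% | 4 | 3 | 1.155 | 1.121 |
| 30% | 4 | 3.5 | 1.129 | 1.113 to 1.115 |

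The 25% row uses 496 subjects and 8 trials; the other rows use 275 per arm. Small excesses over the ceiling are simulation noise. The extreme corner of 30%, 4 kg and 3 kg was not fitted. Its ceiling is √(1 + 0.21 × 16/9) = 1.17, and the fitted ratios at the high end fall below their ceilings.

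**Range for BMI.** With p = 10% to 25%, g = 0.4 to 0.8 kg/m² and s = 1.0 to 1.5 kg/m² (8 trials per cell), ratios ran from 1.001 to 1.043.

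**The case against.** The strongest reply is that nothing rests on these intervals. Weight and BMI at Week 52 carry no test, margin, success rule or precision target, and a slightly wide interval errs on the conservative side. That stands, and it fixes the severity.

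A second reply is that the size is all assumption. This also stands. The documents give none of p, g or s, the upper end needs several unfavourable values together, and the small coefficient depends on variance growing with time. The simulations used complete data and left out genotype and the baseline covariates.

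A third is that the SAP asks only for a similar model, which does not forbid an interaction. True, but none is specified, and a programmer following the text would fit the main effect.

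A reader might also infer more than the documents support:

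- *That the treatment estimate is biased or noisier.* Age is a stratification factor, and with balanced arms and complete data the two models give the same estimate. Only the reported interval is too wide.
- *That BMI suffers as much as weight.* The computed effect is at most about 4%, and negligible over much of the range. BMI z-score also covers BMI in subjects aged 20 or under; weight has no such companion.
- *That the BMI z-score model is at fault for "excluding the term age at screening", since subjects aged 20 or under span both strata.* SAP 8.3.4.1 defines that outcome as already adjusted for age and sex, which is an evident reason to drop the term. No gain from restoring it has been shown.

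**Conclusion.** The point holds as a minor inefficiency in the reported interval, mainly for weight. As written, the model overstates the Week 52 standard error because one age coefficient cannot track growth over seven visits. The weight CI is about 1% to 12% wider than needed across the scenarios run. A mid-range case gives about 5%, falling to about 2% if variance is equal at all visits. For BMI the excess is about 0.1% to 4%. These figures rest on assumed adolescent share, growth and SD, linear growth, age balance between arms and complete data. The treatment comparison remains valid, and no formal conclusion of the trial depends on it.

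**What to change.** In SAP 8.3.4.2, add to the weight paragraph that the MMRM also includes an interaction of age group at screening (under 18 versus 18 and over) with visit. Add the same to the BMI paragraph for consistency, although the gain there is small. Leave the BMI z-score model as it is.

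The cost is (2 − 1) × (7 − 1) = 6 degrees of freedom in a 550-subject model, with no new data and a factor already used in randomisation. SAP section 3 allows an amendment before database lock. A binary age term recovers only the mean growth difference between the two age groups; variation in growth among 12- to 17-year-olds would remain in the error term.
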